#### Time to health-related quality of life/function deterioration

For global health status/QoL, time to deterioration will be defined as the time from the date of randomization until the date of the first clinically meaningful deterioration (a decrease of  $\geq 10$  in the function scales or the global health status/QoL from baseline) or death (by any cause) in the absence of a clinically meaningful deterioration, regardless of whether the patient discontinues study treatment or receives another anticancer therapy prior to global health status/QoL or functional deterioration. Death will be included as an event only if the death occurs within 2 visits of the last PRO assessment where the global health status/QoL or functional change could be evaluated.

Patients whose HRQoL or function (as measured by EORTC QLQ-C30) have not shown a clinically meaningful deterioration and who are alive at the time of the analysis will be censored at the time of their last PRO assessment where the HRQoL/function could be evaluated. Also, if HRQoL/function deteriorates after 2 or more missed PRO assessment visits or the patient dies after 2 or more

missed PRO assessment visits, the patient will be censored at the time of the last PRO assessment where HRQoL/function could be evaluated. If a patient has no evaluable visits or does not have baseline data they will be censored at Day 0. The population for the analysis of time to HRQoL/function deterioration will include a subset of the FAS who have baseline scores of  $\geq 10$ .

#### Symptom improvement rate

The symptom improvement rate will be defined as the number (%) of patients with 2 consecutive assessments at least 14 days apart that show a clinically meaningful improvement (a decrease from baseline score  $\geq 10$  for EORTC QLQ-C30 symptom scales) in that symptom from baseline. The denominator will consist of a subset of the FAS who have a baseline symptom score  $\geq 10$ .

#### HRQoL/function improvement rate

The HRQoL/function improvement rate will be defined as the number (%) of patients with 2 consecutive assessments at least 14 days apart that show a clinically meaningful improvement (an increase from baseline score of  $\geq 10$  for EORTC QLQ-C30 function scales and global health status/QoL) in that scale from baseline. The denominator will consist of a subset of the FAS who have a baseline global health status/QoL or functional score of  $\leq 90$ .

#### **EQ-5D-5L**

The EQ-5D-5L index comprises 5 dimensions of health (mobility, self-care, usual activities, pain/discomfort, and anxiety/depression). For each dimension, respondents select which statement best describes their health on that day from a possible 5 options of increasing levels of severity (no problems, slight problems, moderate problems, severe problems, and extreme problems). A unique EQ-5D health state is referred to by a 5-digit code, allowing for a total of 3125 health states. For example, state 11111 indicates no problems on any of the 5 dimensions. These data will be converted into a weighted health state index by applying scores from EQ-5D value sets elicited from general population samples (the base case will be the United Kingdom valuation set, with other country value sets applied in scenario analyses). Where value sets are not available, the EQ-5D-5L to EQ-5D-3L crosswalk will be applied ([Oemar and Janssen 2013](#)). In addition to the descriptive system, respondents also assess their health on the day of assessment on a visual analog scale, ranging from 0 (worst imaginable health) to 100 (best imaginable health). This score is reported separately.

#### **PGIC**

The PGIC question is “Overall, how would you rate the change in your bladder cancer symptoms since you started this study?” with response options for the PGIC as follows: Very Much Improved (+3), Much Improved (+2), Minimally Improved (+1), No Change

(0), Minimally Worse (-1), Much Worse (-2), and Very Much Worse (-3). No scoring will be done using the assigned numerical values. Instead, the proportion of patients for each response category will be summarized descriptively at each visit.

#### **9.4.1.4 Calculation or derivation of biomarker variables**

All patients must provide an FFPE tumor sample for tissue-based HRR gene panel mutation testing. HRR mutation status has previously been shown to be predictive of response to olaparib in prostate cancer (Mateo et al 2015). The analysis will be performed at a central laboratory testing service using the DNA extracted from FFPE tissue. The tumor sample will be tested for loss of function alterations in 15 pre-specified HRR genes: *ATM*, *BRCA1*, *BRCA2*, *BARD1*, *BRIP1*, *CDK12*, *CHEK1*, *CHEK2*, *FANCL*, *PALB2*, *PPP2R2A*, *RAD51B*, *RAD51C*, *RAD51D*, and *RAD54L*. If the test results indicate that the patient has at least 1 qualifying mutation in any of these genes, the patient will be considered HRRm for the purposes of the study. Patients with no detected mutations will be considered HRRwt.

PD-L1 is a predictive factor for the benefit of durvalumab, with patients with low PD-L1 levels having less benefit. PD-L1 expression will be analyzed retrospectively on a regular basis and adjusted for in the analysis of PFS and OS.

PD-L1 status is determined by the percentage of tumor cells with any membrane staining above background or by the percentage of tumor-associated immune cells with staining (IC+) at any intensity above background. The percent of tumor area occupied by any tumor-associated immune cells (Immune Cells Present [ICP]) is used to determine IC+, which is the percent area of ICP exhibiting PD-L1 positive immune cell staining. PD-L1 status is considered high if any of the following are met:

- $\geq 25\%$  of tumor cells exhibit membrane staining; or
- $ICP > 1\%$  and  $IC+ \geq 25\%$ ; or
- $ICP = 1\%$  and  $IC+ = 100\%$ .

#### **9.4.1.5 Calculation or derivation of pharmacogenetic variables**

In the case of genetic data, only the date that the patient gave consent to participation in the genetic research and the date the blood sample was taken from the patient will be recorded in the eCRF and database. The genetic data generated from the study will be stored in the AstraZeneca Laboratory Information Management System (LIMS) database or other appropriate system. This database is a secure database, which is separate from the database used for the main study. Some or all of the dataset from the main study may be

duplicated within the AstraZeneca LIMS database for exploratory genetic analysis. Data will be reported outside the CSR (see [Appendix D](#)).

### 9.4.2 Efficacy analyses

Efficacy data will be summarized and analyzed using the FAS. All outputs will be summarized by treatment arm.

[Table 17](#) details which endpoints are to be subjected to formal statistical analysis, together with pre-planned sensitivity analyses. Note: all endpoints compare durvalumab + olaparib versus durvalumab + placebo, unless otherwise indicated.

**Table 17 Formal statistical analysis methods and pre-planned sensitivity analyses**

Endpoints analyzed	Notes
PFS	Primary analysis using a stratified log-rank test using Investigator assessment per RECIST 1.1 with the following covariates: 
 
1 HRR status (mutant versus wildtype)
 
2 PD-L1 tumor status (high versus low)
 
3 Bajorin risk index (0 versus 1 versus 2)
 
 Sensitivity analyses using Investigator assessments (RECIST 1.1) 
 
1 Interval censored analysis – evaluation time bias
 
2 Analysis using alternative censoring rules – attrition bias
 

OS	Stratified log-rank test with the following covariates: 
 
1 HRR status (mutant versus wildtype)
 
2 PD-L1 tumor status (high versus low)
 
3 Bajorin risk index (0 versus 1 versus 2)
 
 Sensitivity analysis using a KM plot of time to censoring where the censoring indicator of the primary analysis is reversed – attrition bias
ORR	Logistic regression using Investigator assessment per RECIST 1.1
DoR	KM estimates using Investigator assessments per RECIST 1.1
PFS6	KM estimates of patients alive and progression-free at 6 months
OS18	KM estimates of survival at 18 months

**Table 17 Formal statistical analysis methods and pre-planned sensitivity analyses**

Endpoints analyzed	Notes
Time to symptom deterioration (EORTC QLQ-C30 endpoints)	Stratified log-rank test
Symptom improvement rate (EORTC QLQ-C30 endpoints)	Logistic regression
Change from baseline in symptoms (EORTC QLQ-C30 endpoints)	MMRM analysis

DoR Duration of response; EORTC QLQ-C30 European Organisation for Research and Treatment of Cancer 30-item core quality of life questionnaire; FAS Full analysis set; HR Hazard ratio; HRR homologous recombination repair; HRRm Homologous recombination repair mutant; KM Kaplan-Meier; MMRM Mixed effect model repeat measurement; ORR Objective response rate; OS Overall survival; OS18 Patients alive at 18 months; PD-L1 Programmed death ligand 1; PFS Progression-free survival; PFS6 Progression-free at 6 months; RECIST 1.1 Response Evaluation Criteria in Solid Tumors, version 1.1.

Prior to unblinding for the primary analysis, the proportion of patients in each stratification level will be reviewed, and levels may be combined or factors may be removed from the analyses, if the numbers are too small.

#### 9.4.2.1 Primary endpoint: Progression-free survival

The primary analysis of the primary endpoint PFS will occur when it is expected that approximately 118 PFS events have occurred (79% maturity). PFS will be based on RECIST 1.1 using the Investigator tumor assessments. The analysis will be performed for patients in the FAS population using a stratified log-rank test adjusting for HRR status (mutant versus wildtype), PD-L1 tumor status (defined in Section 9.4.1.4) and Bajorin risk index (0 [defined as no risk factors for metastasis and ECOG performance status] versus 1 [defined as 1 risk factor] versus 2 [defined as 2 risk factors]). The effect of durvalumab + olaparib versus durvalumab + placebo will be estimated by the HR together with its 95% CI from a stratified Cox model (an HR less than 1 will favor durvalumab in combination with olaparib).

KM plots of PFS will be presented by treatment arm, by treatment arm and HRR status (mutant versus wildtype), by treatment arm and PD-L1 tumor status, and by treatment arm and Bajorin risk index where appropriate. Summaries of the number and percentage of patients experiencing a PFS event and type of event (RECIST 1.1 or death) will be provided along with the median PFS for each treatment.

The assumption of proportionality will be assessed.

Sensitivity analyses will be performed to assess possible evaluation-time bias that may be introduced if scans are not performed at the protocol-scheduled timepoints. The midpoint between the time of progression and the previous evaluable RECIST 1.1 assessment will be analyzed using a stratified log-rank test as described for the primary analysis of PFS. For patients whose death was treated as a PFS event, the date of death will be used to derive the PFS time used in the analysis. This approach has been shown to be robust even in highly asymmetric assessment schedules ([Sun and Chen 2010](#)).

Attrition bias will be assessed by repeating the PFS analysis except that the actual PFS event times, rather than the censored times, of patients who progressed or died in the absence of progression immediately following 2 or more non-evaluable tumor assessments will be included. In addition, and within the same sensitivity analysis, patients who take subsequent therapy prior to their last evaluable RECIST 1.1 assessment or progression or death will be censored at their last evaluable assessment prior to taking the subsequent therapy. This analysis will be supported by a KM plot of the time to censoring using the PFS data from the primary analysis where the censoring indicator of the PFS analysis is reversed.

Subgroup analyses will be conducted comparing PFS between durvalumab + olaparib and durvalumab + placebo in the following subgroups of the FAS (but not limited to):

- Sex (male versus female)
- Age at randomization (<65 versus  $\geq$ 65 years of age)
- HRR status (mutant versus wildtype)
- BRCA status (BRCAm versus HRRm, BRCA wildtype versus HRRwt)
- PD-L1 status (high versus low)
- WHO/ECOG performance status (0 and 1 versus 2)
- VES-13 score (<3 versus  $\geq$ 3)
- Visceral disease (lymph-node-only metastasis versus metastatic disease to any other organ system)
- Bajorin risk index (0 versus 1 versus 2)

Other baseline variables may also be assessed if there is clinical justification or an imbalance is observed between the treatment arms. The purpose of the subgroup analyses is to assess the consistency of treatment effect across expected prognostic and/or predictive factors.

Cox proportional hazards modeling will be employed to assess the effect of covariates on the HR estimate. A model will be constructed containing treatment and the stratification factors to ensure that any output from the Cox modeling is likely to be consistent with the results of the stratified log-rank test.

Interactions between treatment and stratification factors will also be tested to rule out any qualitative interaction using the approach of Gail and Simon ([Gail and Simon 1985](#)).

Additionally, for each subgroup, the HR (durvalumab + olaparib:durvalumab + placebo) and 95% CI will be calculated from a Cox proportional hazards model with treatment as the only covariate. These will be presented on a forest plot including the HR and 95% CI from the overall population.

If there are too few events available for a meaningful analysis of a particular subgroup (it is not considered appropriate to present analyses where there are less than 10 events in a subgroup), the relationship between that subgroup and PFS will not be formally analyzed. In this case, only descriptive summaries will be provided.

No adjustment to the significance level for testing of the subgroup and sensitivity analyses will be made, since all of the analyses will be considered supportive of the primary analysis of PFS.

The PFS analysis described above will be repeated for a subset of patients in the FAS with HRRm.

Censoring rules will be provided in the SAP.

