## 9.2 Sample size determination

The study is sized to characterize the PFS benefit of durvalumab in combination with olaparib versus durvalumab monotherapy in first-line patients with unresectable Stage IV UC.

Approximately 150 patients globally will be randomized in a 1:1 ratio to either the durvalumab + olaparib treatment group or the durvalumab + placebo treatment group, 75 patients per arm. The randomization will be stratified based on HRR status (mutant versus wild type) and Bajorin risk index (0 versus 1 versus 2).

The DCO for the primary analysis of PFS will occur when approximately 118 PFS events have occurred across both treatment groups (79% maturity). Assuming a median survival of 3 months for durvalumab monotherapy and recruitment of 150 patients in 6 months, it is estimated that this DCO will occur 7 months following recruitment of the last patient.

If the true PFS hazard ratio (HR) is 0.55 (likely to correspond to an 82% prolongation of PFS), the study will have 90% power to demonstrate a statistically significant difference for PFS at the 2-sided 5% significance level.

The smallest treatment difference that could be statistically significant at the primary analysis of PFS is an HR of 0.69 (assuming a 2-sided p-value of 0.5).

There will be up to 2 analysis timepoints for OS. The first OS analysis will occur at the same time as the primary PFS analysis and will be based on an estimated 44 OS events across therapies (29% maturity), and the second OS analysis will occur when

approximately 100 OS events have occurred (67% maturity). With an approximate 6-month recruitment period and an assumed median OS of 16 months in the durvalumab + placebo arm, it is anticipated that the final analysis will be performed at approximately 27 months after the last patient has been recruited.

Assuming the true OS HR is 0.75, the study will have 30% power to demonstrate a statistically significant OS effect with a 5% 2-sided significance level, allowing for 2 analyses of the data. The smallest treatment difference at the second analysis of OS that could be statistically significant is an HR of 0.68.

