### **Progression-free survival**

PFS (per RECIST 1.1 as assessed by the site Investigator) will be defined as the time from the date of randomization until the date of objective disease progression or death (by any cause in the absence of progression) regardless of whether the patient withdraws from therapy or receives another anticancer therapy prior to progression (ie, date of event or censoring – date of randomization + 1). Patients who have not progressed or died at the time of analysis will be censored at the time of the latest date of assessment from their last evaluable RECIST 1.1 assessment. However, if the patient progresses or dies after 2 or more consecutive missed visits, the patient will be censored at the time of the latest evaluable RECIST 1.1 assessment prior to the 2 missed visits. If the patient has no evaluable visits or does not have baseline data, they will be censored at Day 1 unless they die within 2 visits of baseline; then they will be treated as an event with date of death as the event date.

The PFS time will always be derived based on scan/assessment dates and not visit dates.

RECIST 1.1 assessments/scans contributing toward a particular visit may be performed on different dates. The following rules will be applied:

- For Investigator assessments, the date of progression will be determined based on the earliest of the RECIST 1.1 assessment/scan dates of the component that indicates progression.

- When censoring a patient for PFS, the patient will be censored at the latest of the scan dates contributing to a particular overall visit assessment.

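### The PFS attrition sensitivity analysis changes two censoring rules in one run, so its hazard ratio cannot separate missed-scan attrition from the handling of subsequent therapy (minor)

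*Protocol*

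**What the plan says.** **Primary rule (Section 9.4.1.1, Progression-free survival).** Progression or death counts "regardless of whether the patient withdraws from therapy or receives another anticancer therapy prior to progression". An event that follows two or more consecutive missed visits is censored at the last evaluable assessment before the gap.

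**Attrition analysis (Section 9.4.2.1).** The PFS analysis is repeated with two changes:

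- Change A uses "the actual PFS event times, rather than the censored times, of patients who progressed or died" straight after two or more non-evaluable assessments.
- Change B follows in the next sentence: "In addition, and within the same sensitivity analysis, patients who take subsequent therapy prior to their last evaluable RECIST 1.1 assessment", or before progression or death, are censored at the last evaluable assessment before that therapy.

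**What else is planned.** Table 17 lists two PFS sensitivity analyses. One addresses evaluation-time bias and the other, with alternative censoring rules, addresses attrition bias. Neither A nor B is listed as a run of its own. Section 9.4.2.1 supports the attrition analysis with a Kaplan-Meier plot of time to censoring, built from the primary-analysis data with the indicator reversed. The section ends by leaving censoring rules to the SAP, which is not among the documents reviewed.

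**The concern.** A and B answer different questions. A asks whether discarding events after a scan gap distorted the treatment effect. B replaces the primary handling of subsequent therapy with another. A reduces censoring and B increases it. B's censoring may also be informative, because patients may switch when they are doing badly.

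If the combined HR matches the primary HR, there may be no attrition effect, or there may be two opposite shifts. If it differs, the difference would be reported under attrition bias although switching may have caused it. At stake is how a supportive analysis of the primary endpoint is read, not the primary test.

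**Working it through.** **1. The plan's own figure.** Inputs from Section 9.2: "If the true PFS hazard ratio (HR) is 0.55 (likely to correspond to an 82% prolongation of PFS), the study will have 90% power" "at the 2-sided 5% significance level", and "Approximately 150 patients globally will be randomized in a 1:1 ratio". The Schoenfeld formula for 1:1 allocation is d = 4(z₀.₉₇₅ + z₀.₉₀)² / (ln HR)².

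- d = 4(1.960 + 1.282)² / (ln 0.55)² = 4 × 10.51 / 0.357 ≈ 118.
- With 118 events: ½√118 × 0.598 − 1.960 = 1.287, so power is 0.901.

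The stated 118 events and 90% power reproduce, so the sizing is not in question.

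**2. One patient under each rule (no rates needed).** The patient has a last evaluable scan, stops scanning, starts another therapy, and dies after two missed visits.

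| Rule | Outcome |
|---|---|
| Primary | Censored at the last evaluable scan |
| A only | Death counts |
| A + B as planned | Therapy preceded death, so censored at the last evaluable scan before therapy, the same date as in the primary |

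The combined run leaves this patient uncorrected. Such patients are foreseeable. Section 7.1 stops both drugs on clinical progression without RECIST progression. Tables 1 and 2 and Section 7.1.1 run scans until clinical progression with or without RECIST progression, while the synopsis expects scanning to RECIST progression after clinical progression.

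**3. Size.** From Section 9.2: "Assuming a median survival of 3 months for durvalumab monotherapy and recruitment of 150 patients in 6 months" (the synopsis makes clear that this is median PFS), HR 0.55, and cutoff 7 months after the last patient, so follow-up runs from 7 to 13 months. Scans are 8-weekly to week 48, then 12-weekly.

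Assumed, because the protocol gives nothing:

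- PFS is exponential, and progression is recorded at the next scan.
- A fixed share of each arm misses the two scans at which progression would first have been seen.
- A fixed share switches at a point uniform between 30% and 100% of the time to true progression.
- Missing and switching are independent.

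An unstratified Cox model was fitted to 200,000 simulated patients per arm, with events rescaled to N = 150. The four rules in a row use the same patients. Between rows the primary HR for the same missed-scan rates varies by a few thousandths (0.546 to 0.550), which is simulation noise. With no missing and no switching, the scan-based HR is 0.600 (116 events). That, not 0.55, is the benchmark.

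| Missed (control/combination) | Switch (control/combination) | Primary | A only | B only | A + B |
|---|---|---|---|---|---|
| 5%/15% | 5%/10% | 0.549 | 0.569 | 0.526 | 0.547 |
| 5%/15% | 5%/25% | 0.546 | 0.566 | 0.465 | 0.488 |
| 10%/10% | 15%/5% | 0.595 | 0.603 | 0.619 | 0.625 |
| 5%/15% | 15%/5% | 0.550 | 0.570 | 0.572 | 0.591 |
| 10%/10% | 10%/10% | 0.593 | 0.602 | 0.582 | 0.590 |

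- Row 1: A shifts the HR by 0.569 − 0.549 = +0.020, B by 0.526 − 0.549 = −0.023, and together by −0.002. Events are 105 primary, 113 with A, 97 with B and 104 combined.
- Row 2: A gives +0.020 but the combined run gives 0.488 − 0.546 = −0.058, the opposite direction.
- Row 3: A gives +0.008 and B +0.024. Most of the combined +0.030 comes from switching.
- Row 4: the shifts reinforce each other, +0.041 combined.
- Row 5: with equal rates all four HRs lie between 0.582 and 0.602.

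**The case against.** **The combination has a rationale.** An event restored after a long scan gap may follow another therapy, and censoring at the switch stops that event being credited to randomised treatment. As an alternative rule set this is coherent, and it justifies keeping the combined run as an option. It does not make the result readable as an attrition check.

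**A reader might infer that the analysis is blind to attrition, or that the two changes always cancel.** The documents do not support this. Without rates in the protocol, cancellation is only a possibility, and in row 4 the combined HR moves visibly.

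**A reader might also infer that this is the only planned check on attrition.** It is not. The reverse-censoring plot uses primary-rule censoring and can show whether censoring differs by arm. It gives no HR under alternative handling.

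**A reader might expect olaparib toxicity to drive both missed scans and switching in one arm.** Imbalance is plausible, but several provisions work against it. Section 7.1 allows durvalumab to continue after olaparib or placebo is stopped for toxicity. Section 7.1.1 keeps such patients on all treatment-period assessments, and keeps scans on schedule for those who stop all treatment before RECIST progression. Section 2.1 describes treatment options as limited. The size and direction of any imbalance are unknown, and the 25% switching rate in row 2 is extreme.

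**The analysis is supportive, and the SAP could add separate runs.** Both are true. Section 9.4.2.1 calls its sensitivity analyses supportive, which limits the severity. Leaving censoring rules to the SAP does not undo a combination that the protocol itself fixes.

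**Conclusion.** The point holds in a limited form. The single HR cannot apportion a shift, or an absence of shift, between missed-scan attrition and the handling of subsequent therapy. Patients who stop scanning, switch and then die remain censored as in the primary analysis. Both statements follow from the text.

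The size rests on assumed rates. In row 1 a shift of 0.020 in the HR becomes 0.002 in the opposite direction. For scale, ln(0.569/0.549) = 0.036, against a standard error of the log HR of about 2/√118 = 0.184 at the planned events. The concealed effect is therefore modest unless imbalance is large. The primary test, alpha and sample size are untouched. Severity is minor, and the change is worth making because it is cheap.

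**What to change.** In Section 9.4.2.1 and Table 17, replace the single run with two, reported beside the primary HR:

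- (a) Actual event times after two or more missed or non-evaluable assessments, all else as primary, labelled attrition bias.
- (b) Censoring at the last evaluable scan before subsequent therapy, all else as primary, labelled effect of subsequent therapy.

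Keep the combined run as an option, and keep the reverse-censoring plot. Show the number of patients whose status changes under each rule, by arm. If the protocol is not to be amended, put the split in the SAP before unblinding so that the choice is not driven by data.

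The cost is one extra model run and one table row. No new data are needed, because start dates of subsequent therapy are already collected (Table 2, footnote c).
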